Zip-Stitch[™] for Vaginal Cuff Closure in Laparoscopic Hysterectomy Safety & Efficacy Study

Protocol Number: QD-PRO-045 Rev 005

Principal Investigator: [name] M.D.

IDE Sponsor: ZSX Medical, LLC

Version Number: 5.0

6 March 2020

Summary of Changes from Previous Version:

Primary Affected Section(s)	Summary of Revisions Made	Rationale	
3.1	The primary study efficacy endpoint has been modified to evaluate the occurrence of implant passing events against a performance goal of 5% of patients. FDA requested that the primary endpoint be implant passing e without reference to associate safety/healing events.		
3.1	The primary safety endpoint has been modified to be evaluated through six weeks	FDA requested that dehiscence be valuated through six weeks for the primary endpoint.	
9	Statistical hypotheses have been eliminated. Study sample size rationale has been revised to reflect changes to the primary endpoint and performance goal.	FDA recommendation that comparison to 5% standard can be observational rather than statistical.	

The contents of this protocol are confidential and intended solely for the use of the investigator's team and the IRB/IEC. Do not copy or distribute contents of this document without written permission of ZSX Medical.

TABLE OF CONTENTS

S	TATE	EMENT OF COMPLIANCE	1
1		PROTOCOL SUMMARY	2
	1.1	Synopsis	2
	1.2	Schema	7
	1.3	Schedule of Activities (SoA)	
2		INTRODUCTION	
	2.1	Study Rationale	
	2.2	Background	
	2.3	Risk/Benefit Assessment	
		3.1 Known Potential Risks Associated with Laparoscopic hysterectomy	11
	2.3	3.2 Known Potential Risks Associated with the Use of Zip-stitch™ in	
	La	aparoscopic Hysterectomy	12

1.1 SYNOPSIS

Zip-Stitch[™] for Vaginal Cuff Closure in Laparoscopic Hysterectomy - Safety

& Efficacy Study

IDE Number: G190106/A001

Sponsor: ZSX Medical LLC

[name]

Study Description:This is a prospective, blinded, randomized, controlled study to assess the

safety and efficacy of the Zip-stitch™ System in maintaining vaginal cuff closure following laparoscopic hysterectomy. Participating subjects will be randomized and evaluated for implant passing, successful cuff closure, healing, adverse events, dyspareunia, and pain. Blinded follow-up will involve in-person visits at one week, six weeks, and six months. There will be an additional unblinded follow-up by telephone at 12 months post

operatively.

Objectives: Primary Objective: The primary objective of this study is to evaluate the

efficacy and safety of the Zip-stitch™ Vaginal Cuff Closure system. This will be accomplished by determining the frequency of spontaneous implant passing events and frequency of postoperative vaginal cuff dehiscence, respectively. Primary reporting of both endpoints will take place at six

weeks postoperative.

Secondary Objectives: The secondary objective of this study is to demonstrate the safety and efficacy of the Zip-stitch[™] System as compared to a reference treatment (VICRYL[™]). This will be evaluated by assessing cuff closure and healing, adverse events, changes between pre-operative

and post-operative pain and dyspareunia, and implant passing.

Endpoints: Primary Endpoints:

Efficacy: The primary efficacy endpoint for this study is frequency of implant passing following cuff closure. This will be evaluated through six-

weeks post-operative.

Safety: The primary safety endpoint in this study is frequency of vaginal cuff dehiscence. This will be evaluated through six-weeks post-operative.

Secondary Endpoints (Exploratory):

(1) Binary assessment of cuff closure one, six weeks, and six months after surgery (test versus reference group) based on surgeon

evaluation.

- (2) Binary assessment of cuff healing six weeks and six months after surgery (test versus reference group) based on surgeon evaluation.
- (3) Comparison of implant passing. Percentage of subjects experiencing implant passing will be compared between test and control groups as of the six-week and six-month visits.
- (4) Relationship of implant passing events to adverse events. The frequency of implant passing following cuff closure associated with an Adverse Event will be evaluated through six-weeks post-operative.
- (5) Comparison of incidence of adverse events. Adverse events and serious adverse events will be tabulated for both the test and reference groups.
- (6) Comparison of change in dyspareunia. Non-increase in reported individual subject dyspareunia from baseline to 6-month follow-up will be compared (test versus reference group) using the relevant sexual discomfort module of the Female Sexual Function Index (FSFI).
- (7) Comparison of change in pain. Non-increase in reported individual subject pain from baseline to 6-month follow-up will be compared (test versus reference group) using an 11-point Numerical Rating Scale.

Study Population:

Women above the age of 18 who are undergoing laparoscopic hysterectomy and meet all of the inclusion criteria and none of the exclusion criteria will be eligible for this study.

Sample Size

For the purposes of assessing safety and effectiveness, a target of 59 women will be enrolled in a ratio of 2:1 test to reference (39 test and 20 reference subjects). This is based on a goal of 35 test subjects and an expected 10% of patients lost to follow-up.

Prescreening and informed consent will take place prior to surgery. Enrollment will take place during surgery once it has been confirmed that no intra-operative exclusion criteria are met. Subjects who meet one or more intra-operative exclusion criteria will not be enrolled but will receive standard hysterectomy procedure and follow-up care as they otherwise would.

Inclusion Criteria

- 1. Provision of signed and dated Informed Consent Form
- 2. Stated willingness to comply with all study procedures, including participation in follow-up visits and telephonic follow-up
- 3. Female 18 years or older
- 4. Indicated for Laparoscopic Hysterectomy (may include TLH, LAVH, robotic assisted vaginal hysterectomy)

Exclusion Criteria

Pre-operative Exclusion Criteria

- 1. History of HIV
- 2. History of Hepatitis C

- 3. History of diabetes, that in the opinion of the investigator may delay healing
- 4. Current use of systemic corticosteroids
- 5. Active infection of genitals, vagina, cervix, uterus or urinary tract
- 6. Active bacteremia, sepsis or other active systemic infection
- 7. Presence of Sextually Transmitted Infection (STI)
- 8. Evidence of pelvic inflammatory disease (PID)
- 9. Known clotting defects or bleeding disorders
- 10. Hemoglobin < 8 g/dL
- 11. Metastatic disease
- 12. On anticoagulant therapy
- 13. Participation in another interventional trial
- 14. Pregnancy
- 15. Abnormal PAP results that have not been fully evaluated, or in the opinion of the investigator may indicate risk of abnormal vaginal cuff healing
- 16. Co-morbidities that, in the opinion of the investigator, may indicate risk of abnormal vaginal cuff healing

Intra-operative Exclusion Criteria

- 17. Bowel injury during laparoscopic hysterectomy procedure prior to attempted cuff closure
- 18. Bladder injury during laparoscopic hysterectomy procedure prior to attempted cuff closure
- 19. Cases in which surgeon cannot identify adequate tissue along the cuff to apply suture laparoscopically
- 20. Cases requiring conversion to laparotomy prior to study intervention

Description of Sites/Facilities Enrolling Participants:

The primary sites in this study will be:

Thomas Jefferson University Hospital with locations at [name] and [name]; and

Hershey Medical Center, Penn State College of Medicine at [name].

Enrollment may take place at any of these locations.

There may be additional sites within or outside the United States added (but not more than three total institutions), based upon enrollment.

Description of Study Intervention:

The Zip-stitch™ Vaginal Cuff Closure System is a surgical wound closure system consisting of a series of clips and a reusable, re-sterilizable clip applicator. The clips are made of the bio-absorbable polymer poly-p-dioxanone (PDO) and maintain closure of the vaginal cuff during the healing process, then are ultimately absorbed by the body five to eight months after application.

Protocol QD-PRO-045 Rev 005

Indication for Use:

The Zip-stitch™ System's indication for use is to close the vaginal cuff

following laparoscopic hysterectomy.

Study Duration: Enrollment is intended to occur over three to five months and follow-up is

12-months long. Consequently, this study is expected to take a total of 15 to 17 months from beginning of enrollment to completion of follow-up. Additionally, study blinding will be removed after the last subject completes their six-week follow-up timepoint, and 6 and 12-month follow-up will be collected unblinded. Data will be submitted for regulatory

study follow-up after 6 and 12 months.

Participant Duration: Intervention will occur at the time of surgery and subjects will complete a

12-month follow-up program, including in-person visits at one week, six weeks, and six months, as well as a telephone follow-up at 12-months.

review following unblinding at six weeks, and again after completion of

Statistical Methods: Analysis Populations:

Intent-to-treat population (ITT): This population will include all subjects enrolled and randomized to test or reference treatment. Subjects will be analyzed according to the treatment to which they were randomized,

regardless of the treatment they actually received.

Safety population: This population will include all subjects enrolled and randomized to test or reference treatment. Subjects will be analyzed according to the treatment that they received; patients randomized to the reference arm that receive Zip-stitch™ will be included in the Zip-stitch™ safety population. Similarly, patients randomized to the Zip-stitch™ arm that receive sutures will be included in the reference safety population.

Primary and secondary efficacy endpoint analyses will be performed on the ITT population. All safety analyses will be performed on the Safety population.

Efficacy Analysis:

Unless otherwise stated the analyses of efficacy endpoints will be based on the ITT population as follows.

One-sided endpoint analyses will be performed with 80% statistical power; corresponding *p*-values will be reported, and all two-sided analyses and comparisons between groups will be performed assuming a 0.05 significance level. The corresponding *p*-values and 95% confidence intervals (CIs) will be reported.

Primary Efficacy Endpoint:

Frequency of spontaneous implant passing events will be reported through six weeks. Event frequency will be numerically compared to a performance target of 5%.

Secondary Efficacy Endpoints:

- (1) Cuff closure (compared between test and reference groups) will be assessed (yes or no) by an independent surgeon at one and six weeks, as well as at six months. Fisher's Exact Test will be used to assess possible significance of a difference in cuff closure scores between test and reference groups.
- (2) Cuff healing (compared between test and reference groups), will be assessed (yes or no) by an independent surgeon at six weeks and six months. Fisher's Exact Test will be used to assess possible significance of a difference in healing scores between test and reference groups.
- (3) The percentage of subjects experiencing implant (either clip or suture) passing by six-weeks and by six-months post-operative will be compared between test and control groups using Fisher's Exact Test.
- (4) Frequency of implant passing events determined to be associated with an Adverse Event will be reported through six weeks.

Safety Analysis:

The Safety population will be the analysis population for all safety analyses.

[figure not shown]
Primary Safety Endpoint:

The primary safety endpoint, frequency of vaginal cuff dehiscence, will be reported through six weeks.

Secondary Safety Endpoints:

- (5) The number of adverse events and serious adverse events as well as the proportion of subjects with adverse events, will be summarized by treatment arm, severity, and relatedness to device. Adverse events will be coded using the validated MedDRA system. By-subject listings will be provided for all safety data. Incidence of adverse events will be compared using Fisher's Exact test to assess possible significance of adverse event rate.
- (6) Comparison (test to reference group) of non-increase in subject dyspareunia scores from baseline to 6-months post-operative will be assessed using Fisher's Exact Test.
- (7) Comparison (test to reference group) of non-increase in subject pain scores from baseline to 6-months post-operative will be assessed using Fisher's Exact Test.

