3.2 SECONDARY ENDPOINTS

(1) Binary assessment of cuff closure

Cuff closure will be assessed by an independent surgeon at one and six weeks, as well as at six months. Surgeon visual assessment will grade vaginal cuffs as closed or not closed, or the surgeon may indicate that it was not possible to determine. As such, subjects who experience a dehiscence and are considered a failure in analysis of the primary study safety endpoint will be a failure in this secondary endpoint (lack of closed cuff at six weeks). However, subjects could fail this secondary endpoint without failing the primary study safety endpoint.

In cases in which a surgeon is unable to assess cuff closure, the most recent successful evaluation of cuff closure (including intra-operative evaluation) will be used; reason for inability to determine will be recorded. Fisher's Exact Test will be used to assess possible significance of a difference in cuff closure scores between test and reference groups.

(2) Binary assessment of cuff healing

Vaginal cuff healing will be visually assessed by an independent surgeon at six weeks and six months. Surgeon visual assessment will grade vaginal cuffs as healed or not healed, or the surgeon may indicate that it was not possible to determine. In cases in which a surgeon is unable to assess cuff healing, the most recent successful evaluation of cuff closure will be used. If no prior evaluation has established cuff healing, the cuff will be assumed to have not healed yet. Reason for inability to determine healing will be recorded. Fisher's Exact Test will be used to assess possible significance of a difference in cuff closure scores between test and reference groups. Additionally, healing will be characterized using a predetermined list of binary assessment questions, these will not be statistically compared, but serve to characterize individual healing scores.

(3) Comparison of implant passing rates

The percentage of subjects experiencing implant (either clip or suture) passing by six-weeks and six-months post-operative will be compared between test and control groups using Fisher's Exact Test.

(4) Frequency of implant passing events associated with an Adverse Event

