3.3 EXPLORATORY ENDPOINTS

Cuff closure time

The time required to close the vaginal cuff will be measured from time of conclusion of uterine excision to time of placement of the final Zip-stitch $^{\text{\tiny M}}$ clip or completion of final suture. Comparison may be made between the test and reference group.

Total surgical time

Total surgical time will be calculated based on procedure start and end times (time from first incision to final port closure). Comparison may be made between the test and reference group.

Visibility of implants in the vaginal canal

During visual inspection of the vaginal cuff at each follow-up visit, the surgeon will indicate whether implant material (either clips or suture) can be observed in the vaginal canal. Any association with adverse events, dyspareunia, or pain will also be noted.

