Follow-up will take place in person at one week, six-weeks, and six-months, as well as by telephone at 12-months. Follow-up will be performed by an independent co-investigator who is blinded to the treatment received (investigator who did not complete the procedure and does not have access to the blinded treatment assigned). Data capture will be performed using a validated electronic data capture system (MedNet Solutions, Minnetonka, MN).

Evaluation of the primary study endpoints will be complete after the six-week in-person follow-up visit. Secondary endpoint results will also be collected through the six-month visit and additional data will be collected through 12-months. The primary analysis of the data from this study will be performed when the six-week data are available. Data collected after 6 weeks will be reported in supplemental follow-up reports.

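### Assessor blinding of cuff closure (one and six weeks) and cuff healing (six weeks) is not assured whenever clips or suture are visible at the examination.

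*Combined protocol and SAP*

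**What the plan says.** Section 1.1 (Study Description): "Blinded follow-up will involve in-person visits at one week, six weeks, and six months". Section 4.1 assigns the visits: "Follow-up will be performed by an independent co-investigator who is blinded to the treatment received".

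Section 3.2 sets the two visual endpoints: "Cuff closure will be assessed by an independent surgeon at one and six weeks, as well as at six months"; and "Vaginal cuff healing will be visually assessed by an independent surgeon at six weeks and six months". Each is a yes/no grade, with an option to say that it could not be determined.

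Section 3.3 adds an observation to the same examination. "During visual inspection of the vaginal cuff at each follow-up visit", it says, "the surgeon will indicate whether implant material (either clips or suture) can be observed in the vaginal canal". It continues: "Any association with adverse events, dyspareunia, or pain will also be noted".

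Sections 4.2 and 6.3 describe how blinding is protected. Follow-up data are collected by someone other than the operating surgeon, without access to the assignment or the medical records, and there is a general undertaking to limit unblinding. The only limit on blinding that they admit is that the operating surgeon knows the treatment.

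**The concern.** The safeguards protect the paperwork and not the examination. The test closure is a row of clips and the reference closure is a running suture (Sections 2.2 and 6.1.2). An examiner who sees either one knows how the cuff was closed and, apart from rescue closures under Section 6.5.1, knows the arm. The plan has no separate or masked reader for closure and healing, and no record of whether the assessor became aware of the arm.

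Closure and healing are single visual judgements and so are open to expectation. For closure, an undetermined result is replaced by the last successful evaluation, which may be the intra-operative one (Section 3.2). That one is made by the unblinded operating surgeon (Section 8.1). An assessor who knows the arm therefore has discretion both in the grade and in whether to grade at all. Section 3 says that data through six months may support market clearance, so the description of these results as blinded carries weight.

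**Working it through.** **1. Can implant material be present when the grades are made?** For clips, yes: Section 1.1 says they hold the cuff closed during healing, "then are ultimately absorbed by the body five to eight months after application". They are present at one and six weeks. The documents give no absorption time for the reference suture. Presence is not visibility: Section 3.3 treats visibility as something to be observed, and no section gives a rate.

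**2. Is the grader the person who sees the implant?** No single sentence says so. Sections 3.2, 3.3 and 4.1 read together put closure, healing and implant visibility in one inspection by one blinded surgeon.

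**3. Which assessments are affected?**

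| Visit | Closure | Healing | Blinding status in the plan |
|---|---|---|---|
| One week | graded | not graded | blinded |
| Six weeks | graded | graded | blinded |
| Six months | graded | graded | contradictory |

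For six months, the Study Description in Section 1.1 calls the visit blinded and Section 8.1 places unblinding after all six-month visits. The Study Duration entry in Section 1.1 and Section 6.3 place unblinding after the last six-week visit and call the six-month data unblinded.

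**4. Numbers of women.** The plan's enrolment figure reproduces: 35 / (1 − 0.10) = 38.9, so 39 test; 39 / 2 = 19.5, so 20 reference; 39 + 20 = 59. After 10% loss about 35 test and 20 × 0.90 = 18 reference women are evaluable, 53 in all.

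**5. Weight of one grade.** 1/18 = 5.6 percentage points in the reference arm; 1/35 = 2.9 points in the test arm. Section 9.4.4 defines success for both endpoints as a test failure rate no higher than the reference rate, with no margin, so one grade can decide it.

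**6. Illustration (all rates assumed).** Let the true not-healed rate p be equal in both arms, let clips be visible in a share v of test women, and let the assessor upgrade half of the not-healed test cuffs where clips are seen. The recorded test rate is p × (1 − 0.5v). The chance of success is the sum of Bin(a; 35, p(1 − 0.5v)) × Bin(b; 18, p) over all a, b with a/35 ≤ b/18. Rejection by the two-sided 0.05 Fisher test is summed in the same way.

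| p | v | Recorded test rate | Chance of success | Fisher rejection |
|---|---|---|---|---|
| 5% | 0 | 5.0% | 0.454 | 0.014 |
| 5% | 50% | 3.75% | 0.557 | 0.020 |
| 5% | 100% | 2.5% | 0.683 | 0.028 |
| 10% | 0 | 10.0% | 0.434 | 0.026 |
| 10% | 25% | 8.75% | 0.490 | 0.034 |
| 10% | 50% | 7.5% | 0.552 | 0.045 |
| 10% | 100% | 5.0% | 0.688 | 0.083 |
| 20% | 0 | 20.0% | 0.461 | 0.035 |
| 20% | 50% | 15.0% | 0.632 | 0.066 |
| 20% | 100% | 10.0% | 0.796 | 0.163 |

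The table shows how sensitive the success rule is. It does not estimate what will happen: the documents support no value of v, no upgrade share, and no direction of bias.

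**The case against.** The strongest reply has four parts.

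**The exposure is conditional and does not come from the exploratory item.** Clips are placed laparoscopically and may not show in the vaginal canal. Grading a cuff means looking at it, so any visible material would be seen whether or not Section 3.3 asked about it; that item records the exposure. This stands. A reader might infer that the arm is revealed at every visit, or that a particular number of assessments is unmasked. The documents support neither.

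**The interview outcomes are better protected.** Pain and FSFI answers come from women who are themselves blinded. Section 8.1 lets an investigator or a coordinator collect the visit data, so the interviewer need not be the examiner. Both outcomes are compared between arms only at six months, where the blinding status is itself in doubt. This stands, and the point does not rest on them.

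**The planned output is not silent.** Section 9.4.11 compares implant observation between arms and Section 9.4.9 lists individual data. A reader might infer that any bias is beyond checking, but a cross-tabulation of grades by visibility could be built from the listings. What is missing is a plan to do so and a record of assessor awareness.

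**The stakes are limited.** The Synopsis labels the secondary endpoints exploratory, and Sections 4.2 and 9.2 say they are not powered. Dehiscence requires re-operation (Section 3.1), and a passing event counts only when study personnel confirm the implant (Section 4.2). This stands and limits the severity.

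None of it supplies the missing safeguard. Item order may be set on case report forms that are not in the documents, but no order of items stops an examiner from seeing an implant while grading.

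**Conclusion.** The point holds in a limited form. The plan calls follow-up blinded, but its safeguards do not cover the examiner's own view of the cuff. Assessor blinding is not assured for closure at one and six weeks, or for healing at six weeks, in any woman whose clips or suture are visible. At six months the sections contradict each other, so no blinding claim can be made there until they are reconciled.

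The size is unknown because the visibility rate is not given. What can be said is that the success rule turns on small counts, as steps 5 and 6 show. The conclusion assumes that the surgeon who grades is the one who inspects for implants, as Sections 3.2, 3.3 and 4.1 together imply, and that seen material identifies the arm except after a rescue closure.

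The change is worth making because it is cheap and blinding is a headline feature of the design. The primary endpoints are less exposed.

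**What to change.** 1. At each in-person visit, complete the implant-passing question, adverse event history, pain score and FSFI items before the vaginal examination.
2. On the examination form, record implant visible (none / clip / suture) and whether the assessor became aware of the arm. Do not present the order of items on this form as restoring blinding.
3. Report closure and healing by arm next to the number of unmasked assessments in each arm. Label any split by visibility as descriptive only: visibility arises after randomisation, may differ between clips and suture, and may itself follow healing.
4. Describe the study as subject-blinded, with assessor blinding of closure and healing not assured where implant material was seen.
5. Reconcile the statements on six-month blinding in Sections 1.1, 6.3 and 8.1.

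Cost: a set order for the visit, a short addition to the examination form, one extra table, and a weaker blinding claim on paper. Sample size, endpoints and visits are unchanged.

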3.1 PRIMARY ENDPOINT

(Efficacy) Frequency of Implant Passing Events

Frequency of implant passing events will be reported for all subjects. Failure in this endpoint is defined, on a per patient basis, as the presence of one or more spontaneous implant passing events. A single event may be one or more clips or sutures being spontaneously passed by the patient (*i.e.*, not removed by medical staff).

Frequency of implant passing (either clips or sutures) will be explicitly collected at each follow-up visit; however, events may be reported between visits or during unexpected visits. When implant passing is reported, subjects will be asked to collect and provide passed implants, and an in-person evaluation will be performed. This will involve a visual cuff closure and healing assessment.

In the final analysis of this primary efficacy analysis, the rate of implant passage will be reported through six weeks. The primary objective of this endpoint is to observe a study population failure rate of less than 5% and is neither statistically-driven nor comparative.

(Safety) Frequency of Vaginal Cuff Dehiscence

Vaginal cuff dehiscence is defined as rupture of the surgical wound requiring surgical re-intervention. The proportion of subjects who experience vaginal cuff dehiscence up to six weeks after surgery will be evaluated. In the final analysis of this primary safety endpoint, failure will be reported, and test and control groups will be compared using Fisher's exact test to assess for a possible difference between groups.

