Study recruitment is designed to avoid any potential coercion. Potential subjects will have decided with their doctor to undergo minimally invasive hysterectomy prior to discussing possible participation in this trial. Once a potential candidate has been successfully pre-screened, the informed consent process will be conducted by a study investigator or coordinator other than the potential subject's doctor.

Study enrollment takes place during surgery. Intra-operative enrollment criteria are designed to specifically evaluate closure of the vaginal cuff during laparoscopic hysterectomy, the step Zip-stitch™ is designed for. Subjects who may have unforeseen complications during the anesthesia or colpotomy process for example, are not intended for treatment and their procedure should continue according to standard of care.

Study randomization will take place via blinded, variable block size randomization envelopes stratified by site. Subjects will be blinded to the treatment they receive, but as the operating surgeon cannot be blinded to the treatment provided, this study cannot be fully double-blinded. Every effort will be made to minimize opportunities for unblinding during post-operative data collection. In particular data collection will be performed by a different investigator surgeon without access to the blinded to treatment assignment, including through the electronic data capture system.

Data unblinding will take place after completion of six-week follow-up. This enables reporting of the primary study endpoints and most secondary study endpoints. The data collected at the 6 and 12-month follow-up visit and telephone call are limited to dehiscence, pain, dyspareunia, and adverse events. Adverse events are likely to have significant clinical sequelae, and therefore not likely to be forgotten. Pain and dyspareunia are evaluated based on experience in the time frame of the call, and therefore are not affected by recall bias. No statistical comparisons are being made using 12-month data.

Protocol QD-PRO-045 Rev 005

Some secondary endpoints evaluate incidence and rate of various events; others compare test and reference groups. Comparisons will be made using two-sided Fisher's Exact Tests. Secondary endpoints are not powered to reach statistical significance but are intended to provide additional information and indicate possible safety and efficacy trends.

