9 STATISTICAL CONSIDERATIONS

9.1 STATISTICAL HYPOTHESES

This study will evaluate the hypothesis that more than 5% patients with Zip-stitch™ clips applied to their vaginal cuffs will pass implants. The implant passage rate will be calculated upon conclusion of six-week post-operative follow-up.

The implant passing rate will simply be numerically compared to the established 5% performance target. No formal statistical test will be used to evaluate this hypothesis.

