9.2 SAMPLE SIZE DETERMINATION

The study size was based on FDA's recommendation of the sufficient sample size to support a future 510(k) notification.

A minimum of 30 and a maximum of 40 subjects in the test group have been requested for this study. Assuming a 10% loss to follow-up, a goal of 39 (maximum of 44) subjects are expected to be enrolled in the test group, and a goal of 20 (maximum of 22) are expected to be enrolled in the reference group, for a total goal of 59 (maximum of 66).

No statistical assessment of the rate of successful cuff closure is required for analysis of the primary study endpoints. The rate of implant passing events on a per-patient basis will be numerically compared to the 5% performance target. Nonetheless, the 95% confidence interval will be reported for this endpoint.

This study is also not powered to address secondary endpoints. It is not expected that statistical analyses will yield conclusive results on exploratory endpoints.

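### The synopsis claims one-sided analyses with 80% power, but no endpoint has a one-sided analysis and no power calculation exists

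*Combined protocol and SAP*

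**What the plan says.** The synopsis (Section 1.1, Statistical Methods, Efficacy Analysis) says "One-sided endpoint analyses will be performed with 80% statistical power", with p-values reported. The same sentence goes on to say that "all two-sided analyses and comparisons between groups will be performed assuming a 0.05 significance level". The only alpha in that sentence is therefore attached to two-sided and between-group analyses. The next paragraph of the synopsis describes primary efficacy as a numerical comparison with 5%.

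The body of the protocol says:

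- **Primary efficacy.** Section 3.1 gives the aim as to "observe a study population failure rate of less than 5% and is neither statistically-driven nor comparative". Section 9.1 adds: "No formal statistical test will be used to evaluate this hypothesis". Section 9.2 says of the passing rate: "Nonetheless, the 95% confidence interval will be reported for this endpoint".
- **Secondary endpoints.** Section 4.2 says "Comparisons will be made using two-sided" Fisher's exact tests, and "Secondary endpoints are not powered to reach statistical significance". Sections 9.4.4 and 9.4.5 assign a two-sided Fisher test to each of endpoints 1 to 7.
- **Sample size.** Section 9.2 rests the size on FDA's "recommendation of the sufficient sample size to support a future 510(k) notification", with an allowance for 10% loss to follow-up.

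**The concern.** A power figure means something only when it is tied to an endpoint, a null, an alternative and an alpha. The synopsis gives 80% with none of these, and the sections that define the analyses leave no one-sided test to which it could apply.

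Section 4.1 calls the study pivotal, and Section 3 says its data may support market clearance. Someone who reads only the synopsis would conclude that efficacy is tested one-sided with conventional power, and would expect p-values that no section defines. The clause could also be cited after unblinding to justify a one-sided p-value whose hypothesis and alpha were never fixed in advance.

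**Working it through.** **Step 1: look for the endpoint.** The 80% cannot be reproduced, because the document gives it no inputs. The endpoints compare with the clause as follows.

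| Endpoint | Planned analysis | One-sided test? | Power stated? |
|---|---|---|---|
| Primary efficacy (3.1, 9.1, 9.2, 9.4.2) | Rate against 5%, numerical; 95% CI | No | No |
| Primary safety (3.1, 9.4.3) | Proportion with 95% CI; Fisher test for a difference in 3.1, sidedness not stated | No | No |
| Secondary 1–4 (9.4.4) | Two-sided Fisher | No | Disclaimed (4.2, 9.2) |
| Secondary 5–7 (9.4.5) | Two-sided Fisher | No | Disclaimed (4.2, 9.2) |

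Primary safety also falls outside the synopsis heading under which the clause stands. The acceptance criteria for secondary endpoints 1–4, 6 and 7 are directional: the test-arm failure rate must be no higher than the reference rate. They are numerical rules without an alpha or power, and the test attached to each is two-sided. Endpoint 5 has no acceptance criterion.

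**Step 2: check whether power enters the sample size.** The goal of 35 evaluable test patients with 10% loss gives 35/0.9 = 38.9, so 39. At 2:1, 39/2 = 19.5, so 20, and 39 + 20 = 59. This reproduces the plan's figures with no power term.

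**Step 3: illustration for the reading closest to a one-sided test.** Suppose the clause meant an exact binomial test of a 5% passing rate against a lower one. The plan disclaims such a test, so the alpha, true rates and interval method here are assumptions. The sizes are the requested range (30 to 40), the goal (35), and the enrolment goal and maximum (39, 44). The last two apply only if nobody is lost.

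- Smallest p, zero events: 0.95^n
- p with one event: P(X ≤ 1 | n, 5%)
- Power at an assumed true 1% if only zero events reject: 0.99^n
- True rate at which that rule has 80% power: 1 − 0.8^(1/n)
- Exact two-sided 95% upper limit at zero events: 1 − 0.025^(1/n)

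| n | Smallest p | p, one event | Power at 1% | True rate for 80% | Upper limit |
|---|---|---|---|---|---|
| 30 | 0.215 | 0.5535 | 0.740 | 0.74% | 11.6% |
| 35 | 0.166 | 0.4720 | 0.703 | 0.64% | 10.0% |
| 39 | 0.135 | 0.4129 | 0.676 | 0.57% | 9.0% |
| 40 | 0.129 | 0.3991 | 0.669 | 0.56% | 8.8% |
| 44 | 0.105 | 0.3471 | 0.643 | 0.51% | 8.0% |

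Every smallest p exceeds 0.10, so power is 0 at each size for any alpha up to 0.10. The power and true-rate columns apply only if alpha is large enough to reject at zero events but not at one; 0.215 to just under 0.347 does this at every size. Rejecting with zero events needs at least 45 patients at alpha 0.10 (0.95^45 = 0.0994) and 59 at alpha 0.05 (0.95^59 = 0.0485).

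**Step 4: the between-group reading.** For Fisher's test with 39 against 20, one-sided alpha 0.05 and an assumed 5% rate in the test arm, exact power is 0.095, 0.418, 0.738 and 0.847 at reference rates of 10%, 20%, 30% and 35%. Reaching 80% needs a reference rate between 30% and 35%. The documents state no such alternative.

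**The case against.** The strongest reply is that little turns on this. The next paragraph of the synopsis, and Sections 3.1, 4.1, 9.1, 9.2 and 9.4.2, all describe the primary comparison as numerical, and Sections 4.2 and 9.2 disclaim power for the secondary endpoints. Anyone working from Section 9 would analyse the primary efficacy endpoint as intended. The clause may be left over from before this revision removed formal hypotheses, though that is inference. This is a fair limit on the weight of the point, but it does not make the clause true.

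A second reply is that a separate analysis plan might supply the detail. Section 9.4.10 does refer to one, but only for multiple imputation of rescue cases, and no such text is in the supplied document. The finding covers the supplied text.

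A third is that the power figures concern a test the plan does not intend. That is correct, and they serve only as illustration; the contradiction stands without them. The wide confidence limits are a separate matter of precision, which the plan accepts by declining a formal test.

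**Conclusion.** The concern holds. In the supplied text the synopsis claim of one-sided analyses with 80% power matches no endpoint, no hypothesis, no alpha and no calculation, and it conflicts with Sections 3.1, 4.2, 9.1 and 9.2. This conclusion rests on the wording alone.

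The illustration adds that the claim could not be met against 5% at customary alpha levels: power would be 0 rather than 80% for any one-sided alpha up to 0.10 at 30 to 44 test patients. That part assumes an exact binomial test.

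Severity is low to moderate. The statement should be corrected because it asserts a property the design does not have, but no sample size, endpoint or primary decision rule depends on it.

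**What to change.** In the synopsis, under Efficacy Analysis, delete the clause on one-sided analyses, 80% power and their p-values. Keep the clause that sets 0.05 for two-sided analyses and between-group comparisons. Add one sentence drawn from Sections 9.1 and 9.2, for example: *The sample size follows FDA's recommendation; the primary efficacy rate is reported with a 95% confidence interval and compared numerically with 5% without a formal test; secondary endpoints are not powered.*

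If a one-sided analysis is really intended, Section 9 must instead name its endpoint, null, alternative, one-sided alpha and power calculation.

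The cost of the deletion route is one clause removed and one sentence added. It needs no further patients and changes no endpoint, decision rule or analysis.
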